2.5.3 Handling of missing values/censoring/discontinuations

For patients who prematurely discontinue the study for any reason or patients with missing visits (after baseline), PASI will be imputed using the Last Observation Carried Forward (LOCF) approach. Additionaly non-responder imputation (NRI) analysis will be performed on primary endpoint (i.e., PASI 90 response with logistic regression analysis).

Non-responder imputation rule:

Non-responder imputation will be used: Missing values with respect to response variables based on PASI score will be imputed with non-response regardless to the reason for missing data (e.g. premature study discontinuation, missed visit, administrative issues), exceptions will apply to the following:

• If a subject dropped out the study prior to last scheduled visit and being responders consecutively at least for two preceding visits, the subject will be imputed as responder for the last scheduled visit.

• If a subject who was responder at visit x-1 and visit x+1 but has missing data at visit x, then the subject will be imputed for visit x.

The approach describes above will be adopted also for PASI 90 assessement reported in the extension phase.

The LOCF approach, as well as the NRI approach will be performed for drop-outs and patients with missing visits in between, however no imputation will be done on any visits for patients – entered in the extension phase **and** who have completed the study before reaching 72 weeks.

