	
profiles of secukinumab 300 mg in patients with moderate to severe chronic plaque-type psoriasis, stratified for the presence of HLA-C*06, whose determination will be blinded for patients and investigators. The study will be conducted both on anti-TNFα-naïve and anti-TNFα failure patients and will also stratify for TNFα - 308 polymorphism, BMI, smoking and metabolic syndrome, among others.
 
In addition, through amendment 2 of this protocol, a treatment extension of up to 48 weeks will be offered to willing patients reaching at least a PASI 75 response after 24 weeks of treatment during the core study. The purpose of the treatment extension is threefold; to explore response sustainability to secukinumab after 72 weeks of continuous treatment, to understand if HLA-CW6 can influence the kinetics of the response to secukinumab in the long term, and to generate long-term safety and tolerability data.
 
Furthermore, as a consequence of the European Medicines Agency's (EMA) approval of secukinumab in February 2015 "for the treatment of moderate to severe plaque psoriasis in adults who are candidates for systemic therapy," inclusion criteria have been updated in order to guarantee treatment to systemically naïve patients, as per label.
 
The study extension, for those patients who will enter, can be terminated for any reason by Novartis after a period of at least 12 weeks. Termination may occur only in selected regions where the drug is commercially available; this decision will be made on a region-by-region basis, as for some regions the study will continue as planned even though secukinumab may have become commercially available.

Primary Objective(s) and Key Secondary Objective
	
To evaluate the clinical response in Cw6-negative and Cw6-positive patients treated with secukinumab 300 mg with respect to the Psoriasis Area Severity Index (PASI) 90 response rate after 16 weeks, and thereafter for up to 72 weeks.

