1.1 Study design

This is a multicenter, prospective study involving Cw6-negative and Cw6-positive patients affected by moderate to severe chronic plaque psoriasis.

The study has four periods: a screening period consisting of two visits (pre-screening and screening), an induction period of 4 weeks, a maintenance period of 20 weeks and an extension period of 48 weeks. The schematic of study design is given in Figure 1.1-1 (for Core phase) and in Figure 1.1-2 (for Extension phase) below.

At pre-screening (day -28), patients will be centrally assessed for Cw6 positivity or negativity and stratified into two cohorts (Cw6-negative and Cw6-positive patients). Both patients and investigators will be blinded to the results with respect to Cw6. At the same time 308-TNF α polymorphism will be centrally determined.

After a full screening visit, each eligible patient will be treated according to an induction regimen of two injections of secukinumab 150 mg a week for five weeks starting at baseline (week 0), followed by a maintenance period of one treatment (two injections) per month. At week 16, patients achieving a PASI 50 response will be eligible to continue on secukinumab for an additional 8 weeks. After a total of 24 weeks, willing patients reaching at least a PASI 75 response will enter an extension treatment period of up to 48 weeks. The total duration of the study, including the extension period, is therefore of 72 weeks. For all summaries of "by phases" analyses, total number of patients (N) for extension phase will be the number of patients who have entered the extension. All percentages in extension phase will be based on this N.

Primary analysis time point

The primary analysis will be performed at 16 weeks, and thereafter for up to 72 weeks.

Planned number of patients

The study plans to enroll about 406 adult men or women, of which 365 are evaluable patients, diagnosed with moderate to severe chronic plaque psoriasis for at least 6 months. The patients must be candidates for systemic therapy and may be treatment naïve or have failed to respond to other systemic therapy (including cyclosporine, methotrexate, psoralen combined with ultraviolet A (PUVA) or to an anti-TNFa (or is intolerant and/or has a contraindication to these). The study plans to involve approximately 50 centers. The extension phase will include approximately 306 of the patients initially enrolled in the core study.

Interim analyses

Novartis

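### The SAP's non-responder imputation credits some drop-outs as PASI 90 responders at week 72, and no strict week-72 analysis is specified alongside it

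*SAP*

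**What the plan says.** SAP 2.5.3 makes LOCF the imputation for missing PASI and adds a second approach: "Additionaly non-responder imputation (NRI) analysis will be performed on primary endpoint". The NRI rule begins strictly. Missing responses "will be imputed with non-response regardless to the reason for missing data", and premature discontinuation is among the examples given.

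Two exceptions follow. The second fills a single missed visit when the patient responded at the visits on either side. The first concerns patients who dropped out before the last scheduled visit: "being responders consecutively at least for two preceding visits, the subject will be imputed as responder for the last scheduled visit". It sets no condition on why the patient left and no limit on how long before.

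The section then says: "The approach describes above will be adopted also for PASI 90 assessement reported in the extension phase". It carves out patients who entered the extension and completed the study before week 72; for them there is to be no imputation at all ("however no imputation will be done on any visits for patients").

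Week 72 is not named in the exception. It follows from the schedule: the last extension visit is E4 (Protocol Table 6-2; SAP Table 2.1), and SAP 1.1 states "The total duration of the study, including the extension period, is therefore of 72 weeks". One of the three purposes the protocol synopsis gives for the extension is "to explore response sustainability to secukinumab after 72 weeks of continuous treatment".

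**The concern.** An analysis called non-responder imputation is normally read as the one in which leaving counts as failure. At week 72 this one does not do that for a drop-out with two consecutive responses. Such a patient is a responder under LOCF, because the last value carried forward is a response, and is also a responder under NRI. The two methods then agree for exactly the patients on whom a reader would expect them to differ.

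At stake are the reported week-72 PASI 90 rate and the Cw6 contrast at that visit. If one cohort leaves more often, the effect of that on the week-72 response rate is partly or wholly removed. On one reading of the rule there is also an oddity within a patient. Someone who responds at weeks 20 and 24, enters the extension and leaves at week 30 would be a non-responder at weeks 36, 48 and 60, then a responder at week 72.

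**Working it through.** **1. Is there a strict analysis elsewhere?** The planned approaches to week-72 PASI response are:

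- LOCF (SAP 2.5.3, 2.7.2): carries the last response forward, so it agrees with the exception for these patients.
- NRI (SAP 2.5.3, 2.7.2): includes the exception.
- Observed data, which the SAP calls prevalence (SAP 2.7.2): imputes nothing for drop-outs.
- Drop-out as non-responder (Protocol 9.4.4; SAP 2.5.4): defined for patients without a week-16 PASI, so week 16 only.

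None is specified as counting every drop-out as a failure at week 72.

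**2. Plan's own figures.** The plan states no figure on this point. Its week-16 sample size reproduces, taking 80% response in both cohorts: SE = √(0.16/219 + 0.16/146) = 0.0427; 0.12/0.0427 − 1.96 ≈ 0.85, which is power of about 80%; 365/0.9 gives 406 enrolled. That calculation is not disputed.

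**3. Inputs for the size.** N = 306 extension entrants (SAP 1.1, approximate). The documents give no extension drop-out rate (the only rate stated is 10% at week 16) and no share of drop-outs with two consecutive PASI 90 responses. I assume d = 5% to 20% drop-out and s = 60% to 80% of drop-outs qualifying on responses.

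**4. Wide reading: the two visits are those before drop-out.** Patients credited = N × d × s; shift over strict NRI = d × s.

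- Low: 306 × 0.05 × 0.60 = 9.2 patients; 3.0 points.
- High: 306 × 0.20 × 0.80 = 49.0 patients; 16.0 points.

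**5. Narrow reading: the two visits are weeks 48 and 60.** Only drop-outs after week 60 can qualify. If drop-out is even over the 48 weeks, that is 12/48 = one quarter.

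- Low: 9.2/4 = 2.3 patients; 0.75 points.
- High: 49.0/4 = 12.2 patients; 4.0 points.

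These are upper figures, since under SAP Table 2.1 a PASI from Day 463 falls in the week-72 window and is observed, not imputed. Every patient credited was already a responder at week 60, so the artificial rise from week 60 to week 72 does not occur.

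**6. Cohort contrast, illustration only.** Assume 71% response in week-72 completers of both cohorts (borrowed from the plan's week-16 figure) and drop-out of 5% in Cw6-positive and 15% in Cw6-negative patients.

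| Rule | Positive minus negative, points |
|---|---|
| Strict NRI | 71 × (0.95 − 0.85) = 7.1 |
| SAP rule, wide | 7.1 − 10 × s = 1.1 (s = 0.60) to −0.9 (s = 0.80) |
| SAP rule, narrow | 7.1 − 10 × s/4 = 5.6 to 5.1 |

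The wide reading nearly cancels a difference that arises through drop-out. The narrow reading trims it.

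**The case against.** The strongest reply is that the larger numbers, the week-30 example and the jump at week 72 all need the wide reading. The sentence can as naturally mean the two visits before the last scheduled one. That stands: neither reading can be excluded, which is why both sizes are given.

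The consequence is also limited. The hypothesis and the 12% margin concern week 16, the extension aim is exploratory, NRI is additional to LOCF, and no decision rule rests on NRI at week 72. All of this stands.

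A reader might infer several stronger things that the documents do not support:

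- *That a cohort difference in leaving is hidden.* SAP 2.3.1 reports discontinuation with reasons by cohort and phase, and SAP 2.3 examines cohort differences in reasons for drop-out. Only the effect on the week-72 response rate and contrast is masked.
- *That recorded relapse is counted as sustained response.* The last column of Table 6-2 appears to serve also as an early-termination visit with PASI. A non-response recorded there would normally break the run. The exception mainly reaches patients whose loss of response was never measured.
- *That extension entry ensures two PASI 90 visits.* Protocol 4.3 asks for PASI 75 at week 24 only, so the qualifying share is an assumption.
- *That credited patients were without the drug.* The SAP says they dropped out of the study. Later use of commercial product is unknown.

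One further defence deserves mention. SAP 1.1 bases extension percentages in by-phase summaries on all entrants. If that applied to observed-data response rates, drop-outs would in effect be failures. But the SAP does not say it applies there, and patients who completed early would then count as failures too, which SAP 2.5.3 avoids by leaving them unimputed.

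Finally, counting every drop-out as a failure is one choice among several. That is true, and it is a reason to show the current rule under its own name, not to omit the strict version.

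**Conclusion.** The point holds as a limited one. In the extension, the SAP's NRI is not strict at week 72, agrees with LOCF for the patients it credits, and has no strict counterpart at that visit. Under the assumed 306 entrants, 5% to 20% drop-out and 60% to 80% qualifying, the week-72 rate is raised by 3 to 16 points on the wide reading and by at most 0.75 to 4 points on the narrow one, the latter also assuming even drop-out. The direction follows from the text; the size cannot be taken from the documents. It would be wrong to conclude that the week-16 primary comparison is affected. Patients who completed before week 72 are not part of the problem, since they are not imputed.

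**What to change.** In SAP 2.5.3, for extension visits including week 72, remove the first exception, so that a patient who dropped out is a non-responder at every later scheduled visit. Keep the exception for a single missed visit between two responses, and keep the no-imputation rule for patients who completed before week 72.

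If the current rule is wanted, retain it as a separately named sensitivity analysis. Define *last scheduled visit* (week 24 or week 72, and for whom) and *two preceding visits* (before drop-out, or before the last scheduled visit).

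Cost: one changed sentence, two definitions and one programming flag; no new data. The week-72 NRI rate will be somewhat lower, and patients who left for administrative reasons will count as failures, which the report should say.

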A recently published paper demonstrated an association between the presence of the HLA-C*06 allele and the response to ustekinumab. The study showed an increased response to ustekinumab in Cw6-positive (Cw6POS) patients [PASI 75 at week 12: 96.4% in Cw6POS vs. 65.2% in Cw6-negative (Cw6NEG) patients; P = 0.008] and that HLA-Cw6POS patients

also responded faster to ustekinumab, 89.3% of them reaching PASI 50 at week 4, after a single injection (vs. 60.9% of HLA-Cw6NEG patients). The superior response of HLA-Cw6POS patients was maintained throughout the study period and reached the highest statistical significance for PASI 75 at week 28 (96.35% Cw6POS vs. 72.7% Cw6NEG; odds ratio 9.8). Analysis of TNFAIP3 rs610604 polymorphism and LCE3B/3C gene deletions did not show any significant association with response to ustekinumab (Talamonti M et al. 2013).

Secukinumab is a high-affinity human monoclonal anti-human IL-17A antibody of the IgG1/ κ isotype that demonstrated a favorable safety and tolerability profile with robust clinical activity in a series of Phase II studies, and is undergoing an extensive Phase III program (Gisoni P et al 2014). Secukinumab binds to human IL-17A and neutralizes its bioactivity by inhibiting IL17A produced by both Th17 cells and cells of the innate immune system, thus providing complete anti IL17A blockage. Targeting IL-17A has the potential to reduce autoimmune inflammation while leaving other immune functions undisturbed. While targeting of Th1-promoting or Th17-promoting cytokines affects critical mediators such as IFN- γ , IL-22 and IL-21, selective targeting of IL-17A leaves these Th1/17 activities, as well as certain protective functions of innate cells intact (Patel DD et al. 2013). Furthermore, as a fully human monoclonal antibody, secukinumab has low immunogenicity (i.e., antidrug antibodies) compared to current or emerging biologic therapies that are not fully human. Data linking secukinumab efficacy to a particular genetic biomarker are lacking. However, due to its mechanism of action, the efficacy of secukinumab should not be HLA restricted, and when considering the main haplotype associated with psoriasis, no difference between Cw6-negative and positive patients is expected.

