5.5.12 Early study termination

The study can be terminated at any time for any reason by Novartis. Should this be necessary, the patient should be seen as soon as possible and treated as a prematurely withdrawn patient. The investigator may be informed of additional procedures to be followed in order to ensure that adequate consideration is given to protect the patient's interests. The investigator will be responsible for informing Ethics Committees (ECs) of the early termination of the trial.

The study extension can be terminated by Novartis for any reason after a period of at least 12 weeks. Termination may occur only in selected regions where the drug is commercially available; this decision will be made on a region-by-region basis, as for some regions the study will continue as planned even though secukinumab may have become commercially available.

6 Visit schedule and assessments

Table 6-1 lists all of the assessments and indicates with an "x" when the visits are performed. All data obtained from these assessments must be supported in the patient's source documentation.

Patients should be seen for all visits on the designated day. A time window of ± 2 days for weekly visits and ± 7 days for the monthly visits is allowed.

Patients who discontinue the investigational treatment should also return for the assessments in Table 6-1. If they refuse to return for these assessments or are unable to do so, every effort should be made to contact them or a knowledgeable informant by telephone, reporting it in the source documents.

At a minimum, patients will be contacted for safety evaluations during the 30 days following the last study visit, including a final contact at the 30-day point. Documentation of attempts to contact the patient should be recorded in the source documentation.

Table 6-1: Assessment schedule (core study)

Visit	1	2	3	4	5	6	7	8	9	10	11	12/EoS
Week (relative to baseline)	-4	-2	0 (± 2 days)	1 (± 2 days)	2 (± 2 days)	3 (± 2 days)	4 (± 2 days)	8 (± 7 days)	12 (± 7 days)	16 (± 7 days)	20 (± 7 days)	24 (± 7 days)
Day	-28	-14 to -7	1	7	14	21	28	56	84	112	140	168
Informed consent	X											
Demographic data		X										
Inclusion/Exclusion criteria		X	X									
Smoking history		X										
Medical History		X										
TNF α - 308 polymorphism	X											
Psoriasis: medical history		X										
Previous Psoriasis therapies		X										
Quantiferon TB-Gold (within 3 months)		X										
Physical Examination		X	X	X	X	X	X	X	X	X	X	X

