9.7 Sample size calculation

The primary objective of this study is to evaluate the clinical response in PASI 90 at week 16 of Cw6-negative and Cw6-positive psoriatic patients.

According to literature data, Cw6-positive patients will be about 60% of the entire psoriatic patient population.

From a previous study with ustekinumab (Talamonti et al. 2013) we can observe a difference in response to PASI 90 between Cw6-positive vs Cw6-negative patients of around 30%, in favor of Cw6-POS. Therefore, it is sensible to expect a response in the Cw6-negative cohort not less than 12 % respect to the Cw6-positive group. Further considerations are stated in the paragraph below.

Phase III data on secukinumab show a PASI 90 response at 16 weeks of 71%. Under the assumption that 60% of all the enrolled patient population is represented by Cw6-POS patients, we can reasonably assume to observe a proportion of patients with PASI 90 of 80% in the Cw6-POS cohort.

Under these assumptions, considering a one-side alpha level of 0.025 and a power of 80%, 365 patients (219 Cw6-POS and 146 Cw6-NEG) are sufficient to evaluate if the response in terms of PASI 90 in the Cw6-negative cohort is not less than 12% respect to the Cw6-positive cohort.

Considering a dropout rate at 16 weeks of 10% equally divided in the two studied cohorts, a total of 406 patients should be enrolled.

All calculations were done with NQuery 7.0.

A power analysis based on a different Cw6 patient distribution was made in order to facilitate patient enrollment without power-loss in the primary endpoint evaluation. Table 9-1 shows how the enrollment rate should be set free until the ratio between Cw6-POS and Cw6-NEG reaches the 1:1 rate-distribution, with a power of at least 80%.

In particular, the number of Cw6-POS evaluable patients will range from 219 to 182, whereas those in the Cw6-NEG cohort will range from 146 to 182.

Based on the table below, the enrollment in one of the two cohorts will be stopped when the target number is achieved (a maximum of 244 Cw6-POS patients will be allowed).

Table 9-1: Power analysis

Power	Ratio	Cw6 POS %	Cw6 NEG %	Cw6 POS N	Cw6 NEG N	Overall N	Drop out 10%	
							Cw6 POS N	Cw6 NEG N
80%	0,66	60%	40%	219	146	365	244	163
80%	0,70	59%	41%	215	150	365	239	167
80%	0,72	58%	42%	212	153	365	236	170
80%	0,75	57%	43%	209	156	365	233	174
81%	0,79	56%	44%	204	161	365	227	179
81%	0,82	55%	45%	200	165	365	223	184

81%	0,85	54%	46%	197	168	365	219	187

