2.5 Analysis of the primary objective

The primary objective of this study is to evaluate the clinical response in Cw6-negative and Cw6-positive patients treated with secukinumab 300 mg with respect to the Psoriasis Area Severity Index (PASI) 90 response rate after 16 weeks, and thereafter for up to 72 weeks.

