2.5.2 Statistical hypothesis, model, and method of analysis

The proportion of patients who reach PASI 90 at 16 weeks will be presented with the one-tailed 97.5% confidence interval of the Cw6 positive (POS) – Cw6 negative (NEG) difference.

The null hypothesis:

H0: Cw6 POS - Cw6 NEG \ge 0.12: The difference in proportion of patients achieving PASI 90 response between the Cw6-positive cohort (Cw6 POS) and the Cw6-negative cohort (Cw6 NEG) is at least 12%.

The alternative hypothesis:

HA: Cw6 POS - Cw6 NEG < 0.12: The difference in the proportion of patients achieving PASI 90 response between the Cw6-positive cohort (Cw6 POS) and the Cw6-negative cohort (Cw6 NEG) is less than 12%.

The proportion of PASI 90 response by cohort as well as the difference between cohort together with 97.5% upper CI will be provided using Clopper Pearson CI method.

A logistic regression analysis model will also be fitted, considering age, geographical region (i.e. north vs south vs central), BMI categories (<25 vs >=25), waist circumference, smoking status (Yes vs No), metabolic syndrome (yes vs no), previous PsO therapy (naïve vs previous systemic therapy vs previous biologic therapy), PsA (yes vs no), age at diagnosis of psoriasis, TNF α -308 polymorphism, IGA mod 2011 (severe, moderate, mild) as strata factors.

Model selection:

If model does not converge due to particular covariate(/s), the corresponding covariate(/s) will be removed from the model using Stepwise selection method until model get converged.

Interpretation:

We can conclude that PASI 90 response in the Cw6-negative cohort is not less than 12% with respect to the Cw6-positive cohort if the upper bound of the 97.5 % CI of the difference (Cw6 POS - Cw6 NEG) is less than the non-inferiority margin of 12%.

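### After an early regional closure of the extension, drop-outs are still imputed but patients who stayed are not, so late LOCF and NRI response rates can be distorted under either possible denominator

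*SAP*

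**What the plan says.** Protocol 5.5.12 lets the sponsor end the extension once at least 12 weeks have passed. The decision is made region by region: "Termination may occur only in selected regions where the drug is commercially available". The preceding paragraph of that section covers termination of the study as a whole and says that "the patient should be seen as soon as possible and treated as a prematurely withdrawn patient".

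SAP 2.5 gives the primary objective as the PASI 90 "response rate after 16 weeks, and thereafter for up to 72 weeks". SAP 2.5.3 applies LOCF to patients who discontinue for any reason, adds NRI, and carries both into the extension. It closes with this rule: "The LOCF approach, as well as the NRI approach will be performed for drop-outs and patients with missing visits in between, however no imputation" is made, at any visit, for patients who entered the extension and finished the study ahead of week 72. The NRI rule has an exception: a drop-out who responded at no fewer than two consecutive preceding visits is set to responder at the last scheduled visit.

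SAP 2.7.3 repeats the LOCF rule for the secondary endpoints without the exemption for early completers. SAP 1.1 bases percentages in the extension part of by-phase summaries on the number who entered the extension, and SAP 2.1.1.5 assigns visit-based efficacy data to phases.

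**The concern.** Two groups of patients in a closed region lack data after closure. Those who dropped out earlier are imputed at every later visit. Those who stayed until closure are not imputed at all. The visit could not have taken place for either group, yet the rule treats them in opposite ways.

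The exemption does not name regional closure, but the documents describe no other way to complete before week 72. The text also contains no closure cut-off for drop-outs.

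The late visits carry the stated purposes of the extension: sustainability of response and any long-term influence of Cw6 on its kinetics. They also feed the part of the primary endpoint after week 16, the by-visit PASI 50/75/90/100 summaries, and the IGA 0/1 cohort comparisons under LOCF and NRI (SAP 2.7.2). A fall in response between weeks 36 and 72 could therefore partly reflect who is counted, and a reader of the tables could not tell how much.

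**Working it through.** **The plan's own figure.** The only related figure in the documents is the week-16 sample size (Protocol 9.7): one-sided alpha 0.025, power 80%, margin 0.12, 219 Cw6-positive and 146 Cw6-negative patients. The protocol says "we can reasonably assume to observe a proportion of patients with PASI 90 of 80% in the Cw6-POS cohort". I take 80% in both cohorts because Protocol 1.1 states that "no difference between Cw6-negative and positive patients is expected".

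- SE = √[0.8 × 0.2 × (1/219 + 1/146)] = 0.0427.
- Power = Φ(0.12/0.0427 − 1.96) = Φ(0.85) = 80.2%.
- 365/0.9 = 405.6, so 406 enrolled.

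The figure reproduces. It is untouched by this point: closure needs at least 12 weeks of extension, so it cannot come before about week 24 + 12 = 36.

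**Late visits: assumed inputs.** The documents give no extension drop-out rate and no closure share. Let s be the share of extension entrants in closed regions, T the closure week, and d the drop-out by week 72, uniform over weeks 24 to 72. Drop-out before closure is then d_T = d(T − 24)/48. Stayers respond at r = 85%, and a share q of drop-outs is imputed as responders. As a simplification, the whole region closes at the same study week.

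**Denominator A: patients with an observed or imputed value.**

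- Rate with no closure = (1 − d)r + dq.
- Rate under the rule = {(1 − s)[(1 − d)r + dq] + s·d_T·q} / [(1 − s) + s·d_T].
- Difference = −s·d_T(1 − d)(r − q) / [(1 − s) + s·d_T].

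Week 72, all drop-outs counted as non-responders (q = 0):

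| s | T | d | No closure | Under the rule | Shift (points) |
|---|---|---|---|---|---|
| 0.25 | 36 | 0.10 | 76.5% | 75.9% | −0.6 |
| 0.25 | 36 | 0.20 | 68.0% | 66.9% | −1.1 |
| 0.50 | 48 | 0.10 | 76.5% | 72.9% | −3.6 |
| 0.50 | 48 | 0.20 | 68.0% | 61.8% | −6.2 |
| 0.75 | 48 | 0.10 | 76.5% | 66.5% | −10.0 |
| 0.75 | 48 | 0.20 | 68.0% | 52.3% | −15.7 |

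Third row: 0.5 × 0.9 × 0.85 / (0.5 + 0.5 × 0.05) = 0.3825/0.525 = 72.9%.

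**Effect of q.** The shift is proportional to (r − q)/r. For s = 0.5 and T = 48, with d = 0.10 and 0.20:

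- q = 0.40 (an LOCF case): −1.9 and −3.3 points.
- q = 0.60: −1.1 and −1.8 points.
- q = 0.85: zero.
- q above r would reverse the sign.

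**Week 60.** If the last scheduled visit in the NRI exception is week 72, the exception does not help at week 60. With s = 0.5, T = 48 and d = 0.10, drop-out by week 60 is 0.10 × 36/48 = 0.075. The no-closure NRI rate is 0.925 × 0.85 = 78.6%. Under the rule it is 0.5 × 0.786/0.525 = 74.9%, a shift of −3.7 points.

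**Denominator B: all who entered the extension (SAP 1.1).** Drop-outs are no longer over-weighted, but unimputed stayers remain in the denominator without a response. With s = 0.5, d = 0.10 and q = 0, the week-72 rate is 0.5 × 0.9 × 0.85 = 38.3%, against 76.5%.

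**Cohort contrast.** This uses a second set-up: 10% drop-out, all counted as non-responders, and 75% response in stayers, equal in both cohorts. Suppose 25% of Cw6-positive stayers and 50% of Cw6-negative stayers are closed early.

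- Denominator A: 0.9 × 0.75 × 0.75/(0.9 × 0.75 + 0.1) = 65.3% and 0.9 × 0.5 × 0.75/(0.9 × 0.5 + 0.1) = 61.4%, a spurious difference of 4.0 points before rounding.
- Denominator A, with 35% of drop-outs imputed as responders: 2.1 points.
- Denominator B: 50.6% and 33.8%, a difference of 16.9 points before rounding.
- Equal closure shares: no spurious difference.

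**The case against.** The case against has real force on several points.

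- **Reach.** The only hypothesis, margin and sample size concern week 16. Late visits have no decision rule. This stands.
- **Existing safeguards.** Observed-data results are planned for the primary variable (SAP 2.5.4) and for PASI responses by visit (SAP 2.7.2). They contain no imputed drop-outs, so a divergence would be visible. This stands, but it does not make the LOCF and NRI rates right. The logistic model in SAP 2.5.2 includes north, south and central region. Adjustment on that factor is partial at best, because closure regions are not defined and need not match it.
- **The NRI exception.** It can turn drop-outs into responders at the last scheduled visit, so week-72 figures with q = 0 are the unfavourable end. This stands.
- **The denominator.** If SAP 1.1 governs by-visit efficacy, over-weighting of drop-outs does not occur. That is correct, but the problem then takes the other form shown in the working.

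A reader might also infer that, once a region closes, only its drop-outs represent it. The documents do not support that. Closure would fall on a calendar date, and with staggered enrolment early entrants may already have observed week-60 or week-72 values. The model above is an extreme case in this respect.

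A reader might likewise infer that Protocol 5.5.12 places patients at regional closure among the withdrawn, in direct contradiction of the SAP. That wording sits in the paragraph on terminating the whole study, and the paragraph on the extension does not repeat it. It calls for clarification and is not an established conflict.

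**Conclusion.** The asymmetry is in the SAP text, and it can distort LOCF and NRI response rates at visits after a regional closure, from about week 36 to week 72. The form depends on a denominator that the SAP does not settle for by-visit efficacy: over-weighted drop-outs, or stayers counted as non-responders. The cohort contrast is affected only if closure or drop-out differs between cohorts.

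The size cannot be fixed from the documents. The illustrative week-72 range of −0.6 to −15.7 points rests on the assumed closure shares, closure weeks and drop-out rates in the table, on denominator A, and on every drop-out counting as a non-responder. It is a range of examples and not a bound. It shrinks, possibly to nil, as more drop-outs are imputed as responders.

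It would go too far to say that late PASI 90 will fall because of this rule. That needs closure to happen on some scale and drop-outs to be imputed at a lower response than stayers, and the documents establish neither. The week-16 test, its sample size and the observed-data summaries are unaffected. The change should be made before the late visits are analysed, but the main conclusion does not depend on it.

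**What to change.** - **SAP 2.5.3 and 2.7.3:** state that a visit whose scheduled date for that patient falls after the calendar date of extension closure in the patient's region is treated as not scheduled, and is not imputed for any patient, drop-out or early completer. Impute drop-outs only up to the last visit that could have taken place before closure.
- **SAP 1.1:** for by-visit efficacy percentages in the extension, use as denominator the patients whose visit could have taken place, and amend the by-phase sentence to match. Without this, the change to the imputation rule leaves the second distortion in place.
- **Classification:** state that patients who stay to regional closure are administrative completers. Clarify in Protocol 5.5.12 that the wording on premature withdrawal does not reclassify them for imputation.

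If closure is unrelated to drop-out and response, this returns the share of drop-outs at each late visit to its true value. The cost is a few sentences, one closure date per region in the analysis data, and fewer imputed records at the late visits.
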